Hypothesis 1A: We hypothesize that an enhanced version of the SleepTrackTXT tool that includes sleep health and sleep quality components will contribute to significant reductions in intra-shift fatigue.

Aim 2: To determine the impact of the SleepTrackTXT intervention on sleep quality and sleep health indicators including hours of sleep and recovery between shift work.

Rationale Aim 2: Preliminary findings from our pilot randomized trial using an Intent-To-Treat analysis shows a statistically significant improvement in sleep quality among participants in the intervention group. The improvement fell short of a cut point thought to be clinically meaningful. We believe an enhanced intervention focused on sleep debt may have a greater impact on sleep quality.

Hypothesis 2A: We believe an enhanced version of our brief SleepTrackTXT intervention that includes a sleep health and sleep quality component can lead to clinically meaningful improvements in sleep quality over time.

Our power calculation was designed to determine the number of subjects needed to detect a clinically meaningful difference of 3 points on the PSQI from baseline to the study end. We fixed alpha at 0.05 and performed one-sided hypothesis testing. The standard deviation of the difference was estimated as 2.2 using data from our recent randomized trial.[5] Group sample sizes of 27 for the intervention and 27 for the control group achieve 90% power to reject the null hypothesis of equal means with a standard deviation of 2.2 and significance level of 0.05 using a two-sided two-sample equal variance t-test. We estimate a 15% attrition rate based on our prior randomized trial.[23] We estimate 15% of participants in the intervention group will not abide by the intervention protocol. Based on these estimates, we seek to enroll a total of n=100 (50 per group) to account for attrition and non-compliance.

Research Protocol, Part Three – Methods (3000 characters):

STUDY DESIGN: We will use a two-arm parallel, randomized, controlled and single-blinded trial. Our design is similar to the original SleepTrackTXT trial with 100 EMS clinicians.[5, 23]

SETTING AND POPULATION: We will recruit and enroll study participants from four air-medical EMS organizations: 1) Carolina's MedCenter Air; 2) STAT MedEvac; 3) MedFlight of Ohio, and 4) MercyFlight of Buffalo, NY.

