CONTROL GROUP: The control group participants will use an online sleep diary, a shift scheduling tool to document shift schedules, answer text-message queries about their fatigue and sleep health between shifts (inter-shift) and during shiftwork (intra-shift). The intra-shift text-messages are modeled after the original SleepTrackTXT trial (clinicaltrials.gov identifier: NCT02063737). Control group participants will receive inter-shift messages on days off from work at noon (12:00pm). These inter-shift messages will query the participant's sleep obtained, perceived recovery since last shift, fatigue, sleepiness, and difficulty with concentration. A select group of n=10 control group participants will wear wrist actigraphy for purposes of validating self-reported sleep diary information. This same select group of 10 control group participants will be asked to complete psychomotor vigilance tests (PVTs) at the beginning and end of a select number of shifts during the study period.

Research Protocol, Part Four – Outcome Measures & Data Analysis (3000 characters):

One outcome of interest (linked to Aim 2) is sleep quality, which will be measured with the widely used Pittsburgh Sleep Quality Index (PSQI).[19] A PSQI score of 6 or more on a 21-point scale indicates poor sleep quality. A reduction in PSQI of 3-points suggests a clinically meaningful improvement in sleep quality.[22] We will administer the PSQI at baseline and then again at the end of the 4-month study period.

Our power calculation was designed to determine the number of subjects needed to detect a clinically meaningful difference of 3 points on the PSQI from baseline to the study end. We fixed alpha at 0.05 and performed one-sided hypothesis testing. The standard deviation of the difference was estimated as 2.2 using data from our recent randomized trial.[5] Group sample sizes of 27 for the intervention and 27 for the control group achieve 90% power to reject the null hypothesis of equal means with a standard deviation of 2.2 and significance level of 0.05 using a two-sided two-sample equal variance t-test. We estimate a 15% attrition rate based on our prior randomized trial.[23] We estimate 15% of participants in the intervention group will not abide by the intervention protocol. Based on these estimates, we seek to enroll a total of n=100 (50 per group) to account for attrition and non-compliance.

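### Enrolment of 50 per group does not follow from 27 per group with 15% attrition and 15% non-compliance, and 27 is not the size for a 3-point PSQI difference; the result is surplus enrolment, not lost power

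*Combined protocol and SAP*

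**What the plan says.** The same sample-size paragraph stands in Research Protocol, Part Two (Objectives Hypotheses) and Part Four (Outcome Measures & Data Analysis). Its steps are:

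- **Effect.** The aim is to "detect a clinically meaningful difference of 3 points on the PSQI from baseline to the study end".
- **Variability.** "The standard deviation of the difference was estimated as 2.2 using data from our recent randomized trial".
- **Test.** First "We fixed alpha at 0.05 and performed one-sided hypothesis testing"; two sentences later "significance level of 0.05 using a two-sided two-sample equal variance t-test".
- **Base size.** "Group sample sizes of 27 for the intervention and 27 for the control group achieve 90% power to reject the null hypothesis of equal means".
- **Allowances.** 15% attrition, with no arm named, and then "We estimate 15% of participants in the intervention group will not abide by the intervention protocol".
- **Enrolment.** "we seek to enroll a total of n=100 (50 per group) to account for attrition and non-compliance", introduced as resting on those estimates.

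No inflation formula is shown. The 90% power is attached to 27 per group; no power is stated for 50. Part Four describes a linear mixed model for end-of-shift fatigue but names no analysis population for the PSQI. Intention-to-treat is mentioned once, in the rationale for Aim 2, to describe how the pilot was analysed.

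**The concern.** The sentence on enrolment claims a derivation: "Based on these estimates, we seek to enroll a total of n=100 (50 per group"). A reader should be able to start from 27, apply the two 15% allowances and arrive at 50. If that cannot be done, the reader does not know which effect or which power the enrolment figure stands for.

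The non-compliance allowance adds to the uncertainty. It applies to the intervention group only, yet both groups are raised to 50. Non-compliance can be allowed for in two ways. Participants can be left out and replaced by number, or they can be kept in their assigned group with a smaller expected effect. The two ways need different arithmetic and answer different questions, and the plan does not say which it uses. What is at stake is whether the sample-size justification can be reproduced, and what analysis it refers to.

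**Working it through.** **Inputs, all from the power paragraph:** difference 3 points; SD 2.2; alpha 0.05; 27 per group; 90% power; attrition 15%; non-compliance 15% in the intervention group; 50 enrolled per group. Power is from the noncentral t distribution for a two-sample equal-variance test, with noncentrality = difference / (SD × √(2/n)).

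**1. The plan's base figure (27 per group, 90% power).**

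| Difference, SD 2.2 | Test | n per group for 90% | Power at 27 per group |
|---|---|---|---|
| 3 points | two-sided 0.05 | 13 (91.5%; 12 gives 89.1%) | 99.8% |
| 3 points | one-sided 0.05 | 10 (90.1%) | over 99.9% |
| 2 points | two-sided 0.05 | 27 (90.6%; 26 gives 89.5%) | 90.6% |
| 2 points | one-sided 0.05 | 22 | 95.1% |

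For 3 points at n = 27 the noncentrality is 3 / (2.2 × √(2/27)) = 3 / 0.599 = 5.01, far above what 90% power needs. The smallest difference that 27 per group detects with 90% power, two-sided, is 1.98 points. So 27 does not reproduce from 3 points under either sidedness, but it matches 2 points, two-sided. Reading 2.2 as the SD at a single time and multiplying by √2 gives 24 per group for 3 points, again not 27.

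**2. The step from 27 to 50.**

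| Route | Arithmetic | Per group |
|---|---|---|
| Attrition only | 27 / 0.85 = 31.8 | 32 |
| Both as losses, multiplied | 27 / (0.85 × 0.85) = 37.4 | 38 |
| Both as losses, added | 27 / (1 − 0.30) = 38.6 | 39 |
| Marked up instead of divided | 27 × 1.30 = 35.1; 27 × 1.15² = 35.7 | 36 |
| Attrition plus dilution of the effect | 27 / (0.85 × 0.85²) = 43.96 | 44 |

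The last row keeps non-compliers in the analysis. The effect falls by the factor 0.85, so the required n rises by 1/0.85². None of these gives 50. Working back, 1 − 27/50 = 46% would have to be lost. Less usual combinations overshoot: 27 / 0.85⁴ = 51.7 and 27 / 0.70² = 55.1.

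**3. What 50 per group delivers.** Completers: 50 × 0.85 = 42.5, taken as 42 per group. Standard error: 2.2 × √(2/42) = 0.480. Two-sided 0.05:

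- Difference detectable with 90% power: 1.57 points.
- 3 points among compliers, diluted: 3 × 0.85 = 2.55 points, power 99.95% (99.87% if the extra variance from mixing compliers and non-compliers is added).
- 2 points among compliers, diluted: 2 × 0.85 = 1.70 points, power 93.8% (92.7% with the extra variance).

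**4. Sensitivity to the SD.** The plan calls 2.2 the SD of the difference. If it were instead the SD at a single time and the SD of change were 2.2 × √2 = 3.11, power at 42 per group would be 96.0% for 2.55 points and 69.7% for 1.70 points. This is a sensitivity case, not a reading that the text supports.

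**The case against.** The strongest reply is that nothing is lost. Enrolling above a calculated minimum is common. Fifty exceeds every standard inflated figure (32 to 44), and power at the plan's SD exceeds 90% for the 3-point effect and even for a 2-point effect after dilution. That stands, and it limits the point to an unreproducible justification with surplus enrolment. It does not remove the point, because the plan presents 50 as the result of its estimates and gives no other reason for it.

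Three stronger readings are tempting, and the documents do not support them.

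- *Non-compliers are to be dropped, so the comparison is biased.* A reader might infer this from an allowance that covers one arm and is set beside attrition. The text says only that the target accounts for non-compliance, and raising n because the effect is diluted fits the same words. The arithmetic does not reveal exclusion either: counting non-compliers as lost gives 38 or 39, further from 50 than dilution does. Any inflated type I error worked out from this would need both an exclusion that the plan does not state and an assumed worse outcome in non-compliers. What stands is that the handling is unspecified.
- *The trial fails to deliver its stated 90% power.* The 90% belongs to 27 per group. No power is stated for 50 that could be missed.
- *The correct enrolment is 44 per group.* That holds only if 27 is sound, and it is not the size for 3 points. With 2.55 points as the diluted effect, 17 completers, or 17 / 0.85 = 20 enrolled per group, would give 90% power. Forty-four belongs to a 2-point effect.

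**Conclusion.** The concern holds as a failure of the sample-size justification at two steps. Neither the base size nor the inflation reproduces from the stated inputs: 27 per group where 13 (two-sided) or 10 (one-sided) would do for 3 points, and 50 per group where 27 with the two allowances gives 32 to 44. The paragraph also contradicts itself on sidedness, and the plan leaves the PSQI analysis population unnamed. The discrepancy is in the safe direction for power, so enrolment need not change.

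The delivered-power figures assume SD 2.2 in both groups, attrition of 15% in each arm that removes the end-of-study PSQI, no effect in non-compliers, and two-sided 0.05. The 2-point match to 27 is an observation about the numbers. The documents do not say that 2 points was the intended difference.

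**What to change.** Keep n=100. In both Part Two and Part Four, replace the derivation with wording such as:

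> All randomised participants are analysed in their assigned group. With 50 per group and 15% attrition (42 per group), the trial has 90% power at two-sided 0.05 for a PSQI difference of about 1.6 points (SD 2.2). A 3-point effect among compliers, diluted to 2.55 points by 15% non-compliance, has over 99.9% power.

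In the same edit:

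- Correct the statement that 27 per group gives 90% power by giving the effect it belongs to, or remove it.
- Use one sidedness throughout. The figures above are two-sided.
- Report any analysis restricted to compliers as secondary.
- Do not substitute 44 per group, since it inherits the unexplained 27.

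The cost is wording in two places, with no change to enrolment or conduct. The one downside is that the effect stated for the as-randomised analysis becomes 2.55 points, not 3.

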Site 4: Mercy Flight of Buffalo, NY. Mercy Flight operations are conducted from three bases (Buffalo, Olean and Batavia), 24 hours a day / 7 days a week. The Mercy Flight Team consists of 26 paramedics, 27 nurses, 13 pilots, 9 air medical communications specialists, 6 aircraft mechanics and an 11 member administrative, development, finance and facilities management team that provides the necessary support service for flight operations. Each helicopter crew consists of a Pilot, Paramedic and Nurse. Flight Paramedics have at least two years of high volume, critical care EMS experience. Flight Nurses have more than 2 years of critical care experience in an Emergency Room (ER), Intensive Care Unit (ICU) or other critical care field. Over the past 30+ years, Mercy Flight has conducted more than 20,000 patient missions and thousands of Ground Crew Safety Training and Community Education sessions throughout its primary service area of Western New York, Northwest Pennsylvania and Southern Ontario. The dispatch center is staffed 24/7 by Communications Specialists who field, prioritize, dispatch and coordinate incoming flight requests. They are certified by the National Association of Air Medical Communication Specialists (NAACS). Mercy Flight a Part 145, FAA Certified Repair Station and our in-house aircraft mechanics utilize more than 100 years of combined experience to keep the helicopters flight-ready.

PROTOCOL: We will recruit via email and study flyers sent directly to eligible individuals employed at the study sites. We seek to enroll n=100 clinicians. Clinicians with an interest in the study will complete a telephone screening appointment. Inclusion criteria include: 1) 18 years of age and older, 2) working clinically at a study site, 3) currently working in shifts, 4) has a smartphone, and 5) willing to take part in a research study that requires the sending and receiving of multiple text messages daily over 4-months. Eligible clinicians will complete a standard enrollment process with an IRB-approved informed consent procedure.

Randomization into the intervention versus control groups will occur immediately after completion of informed consent. All consented participants will receive a unique login account to access the study website. Participants will use the secure study website to document shift schedules for four months. Participants will receive \$100 remuneration.

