One outcome measure is linked to Aim 1 and is intra-shift fatigue reported at the beginning, during, and end of scheduled shifts. We will use a single-item measurement of fatigue, which is the preferred approach for research that involves real-time data capture and/or ecological momentary assessment (EMA).[20] This measure was constructed based on prior EMA research of insomnia, it has been tested in our pilot trial and shown to be sensitive to change in fatigue over the course of shift work.[21] We hypothesize that over time and after repeated exposure to the intervention, participants in the intervention group will report lower levels of fatigue at the end of shift than participants in the control group.

We will use linear mixed-model analyses to examine the effectiveness of the intervention on reducing reported fatigue at the end of shift among participants in the intervention group and compare reported values to the control group. We will construct a model where the outcome is the reported fatigue at the end of each shift, a fixed effect of time in study, and a random effect for participants to account for multiple shifts within each person. We will examine the estimated change in fatigue per shift and over multiple shifts throughout the study period. Post-estimation testing will be used to describe the correlation in fatigue scores within the subjects across shifts.

Independent measures of interest include age, sex, health status indicators, and other demographic and person-level variables that address employment status, shift schedule/pattern, general fatigue, co-morbidities/diagnoses, and psychosocial factors that may be associated with sleep and shiftwork. We will use descriptive statistics to examine the distribution of these variables, parametric and non-parametric tests to assess change in values/scores on measures that may change over the course of the 4-month study period.

Research Protocol, Part Five – Limitations (3000 characters):

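### The Aim 1 model names no baseline covariate although baseline PSQI is planned, so the arm difference in mean end-of-shift fatigue may be less precise than the collected data allow

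*Combined protocol and SAP*

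**What the plan says.** The Aim 1 analysis is in Research Protocol, Part Four. In the linear mixed model "the outcome is the reported fatigue at the end of each shift, a fixed effect of time in study" is followed by "a random effect for participants to account for multiple shifts within each person". The stated purpose is to "compare reported values to the control group", but the sentence that sets out the model contains neither an arm term nor an arm-by-time term. The hypothesis reads: "over time and after repeated exposure to the intervention, participants in the intervention group will report lower levels of fatigue at the end of shift".

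The same part says of the Aim 2 outcome: "We will administer the PSQI at baseline and then again at the end of the 4-month study period". No role in Aim 1 is given to the baseline value.

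Other person-level variables are listed: "Independent measures of interest include age, sex, health status indicators, and other demographic and person-level variables", continuing to "shift schedule/pattern, general fatigue, co-morbidities/diagnoses" and psychosocial factors. The only uses described for them are descriptive summaries and tests of change over the study, so this list does not bring covariate adjustment into the Aim 1 model.

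Part Three says: "Randomization into the intervention versus control groups will occur immediately after completion of informed consent". It does not say whether the baseline PSQI is completed before or after that step.

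**The concern.** When each person contributes many shifts, shift-to-shift noise largely averages out. What remains in the variance of an arm mean is mostly stable differences between people, and a person-level baseline covariate can remove part of that.

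Baseline PSQI is a natural candidate. Hypothesis 1A expects sleep-quality content to lower intra-shift fatigue, which presumes that the two are related. PSQI is also the one person-level measure whose baseline administration is stated outright. If it is prognostic, leaving it out gives a wider confidence interval for Aim 1 than the planned data require. Naming the covariate in advance also avoids a later choice among the many variables listed. The stake is precision, not validity.

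**Working it through.** **Plan's own figure.** None exists for Aim 1. The documents give no power, precision, fatigue SD, intraclass correlation (ICC) or PSQI-fatigue correlation. The only sample-size calculation is for PSQI in Aim 2 and does not bear on this point.

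**Inputs from the documents**
- Shifts per person (m): the Abstract reports 2,621 pilot shifts from 100 people over 90 days, so 2,621/100 = 26.2. Scaled to four months, 26.2 × 120/90 = 34.9. Range used: 26 to 35.
- People per arm (n): 50 enrolled. With 15% attrition, 50 × 0.85 = 42.5. Range used: 42 to 50.

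**Assumptions**
- ICC of end-of-shift fatigue: 0.2 to 0.6.
- Correlation r between baseline PSQI and a person's usual end-of-shift fatigue: 0 to 0.5.
- A random-intercept model with an arm term added, because the plan writes none.

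**Formulae (total variance set to 1)**
- Without the covariate, the variance of the arm difference is proportional to V0 = ICC + (1 − ICC)/m.
- With it, V1 = [ICC(1 − r²) + (1 − ICC)/m] × [1 + 1/(2n − 4)]. The last factor is the price of estimating the covariate's coefficient.
- The SE ratio is √(V1/V0).

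**Share of variance that is between people.** At ICC 0.2 and m = 26: 0.2/(0.2 + 0.8/26) = 0.87. At ICC 0.6 and m = 35: 0.6/(0.6 + 0.4/35) = 0.98.

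**Worked case: n = 42, m = 35, ICC 0.4, r = 0.3**
- V0 = 0.4 + 0.6/35 = 0.4171
- V1 = (0.4 × 0.91 + 0.6/35) × (1 + 1/80) = 0.3811 × 1.0125 = 0.3859
- V1/V0 = 0.925; SE ratio = 0.962, so the SE is 3.8% smaller.

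**Over the whole range of n, m and ICC**

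| r | V1/V0 | SE of the arm difference in mean level |
|---|---|---|
| 0 | 1.010 to 1.012 | 0.5 to 0.6% larger |
| 0.1 | 1.001 to 1.004 | 0 to 0.2% larger |
| 0.2 | 0.971 to 0.977 | 1.1 to 1.5% smaller |
| 0.3 | 0.921 to 0.934 | 3.4 to 4.0% smaller |
| 0.4 | 0.852 to 0.872 | 6.6 to 7.7% smaller |
| 0.5 | 0.763 to 0.793 | 11 to 13% smaller |

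Setting V1 = V0 in the worked case gives r² = (0.4171/0.4) × (1/81) = 0.0129, so break-even is near r = 0.11.

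**Simulation check.** Mixed models were fitted to simulated data with 50 per arm, 26 shifts and ICC 0.4, using 60 replicates at each r. For the mean-level contrast the SE ratios were 1.005, 0.953 and 0.883 at r = 0, 0.3 and 0.5. The formula gives about 1.005, 0.961 and 0.878. For the arm-by-time contrast the ratio was 1.000 at every r, because a main effect of a person-level covariate does not change the precision of a slope difference in this model.

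**The case against.** The strongest reply is that this is a preference and not a defect. Four parts of it stand.

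- **The gain is not established.** The documents treat poor sleep and fatigue as related but never quantify the relation between PSQI and the single-item score. A reader might infer that precision is certainly being lost, or lost heavily. With 35 shifts, ICC 0.3 to 0.5 and 84 completers, a 15% smaller SE needs PSQI to explain 30% of between-person variance, a correlation of √0.30 = 0.55. Nothing in the documents supports that figure.
- **The contrast may be a slope.** The hypothesis speaks of an effect that emerges with repeated exposure, and the analysis is also to look at change over shifts. If the Aim 1 test is arm-by-time, a PSQI main effect adds nothing. The hypothesis also predicts lower levels at end of shift, so a mean-level contrast is a legitimate reading, though not the only one.
- **The model sentence omits treatment itself.** It may be a sketch in a length-limited section and not a full covariate list. The missing arm term is the larger gap, because without it the contrast whose precision is at issue is undefined.
- **No bias follows.** A reader might infer that chance imbalance in baseline sleep quality invalidates the unadjusted result. It does not: randomization balances the arms on average, and the unadjusted interval already allows for chance imbalance.

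It can also be said that general fatigue, which the plan lists, is closer to the outcome than PSQI. That is fair, but the documents do not say when it is measured. Beginning-of-shift fatigue is recorded after randomization and would not be a suitable baseline covariate.

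None of this gives the Aim 1 model a baseline covariate. The omission remains in the text, and the most that adjustment could cost in precision is small.

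**Conclusion.** The point holds as a low-cost efficiency improvement, not as an error in the plan. The Aim 1 model as written leaves out a baseline value that the plan intends to collect, and the arm difference in mean end-of-shift fatigue may be less precise as a result.

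The size depends on an unreported correlation: negligible at 0.1 or below, modest at 0.3 (equivalent to 7 to 9% more participants, from 1/0.934 to 1/0.921), and material only towards 0.5. These figures rest on the assumed ICC, the pilot shift rate and a random-intercept model. They apply to a difference in mean level only.

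**What to change.** In Part Four:

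1. Write the arm term, and the arm-by-time term if that contrast is intended, into the Aim 1 model.
2. Prespecify baseline PSQI, as a continuous fixed covariate, in that model.
3. Require the baseline PSQI to be completed before the arm is disclosed.
4. Report the adjusted between-arm difference in mean end-of-shift fatigue.

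The analysis cost is one degree of freedom, about 0.6% in SE if PSQI proves unrelated to fatigue. No new data are needed. There may be a small procedural cost: because randomization follows consent immediately, the order of consent, baseline PSQI and disclosure of the arm would have to be set out in Part Three.

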SIGNIFICANCE: There is limited real-time fatigue monitoring of EMS clinicians. However, there is growing enthusiasm and preliminary data to support use of real-time fatigue monitoring using mobile technologies such as cell phones and smartphones.[15, 16] Most Americans (90%) own a cell phone and half own a smartphone.[17, 18] Most cell phone owners (80%) send or receive text-messages.[17] A recent systematic review of intervention studies using text-messages or mobile applications showed a positive impact on behaviors, such as smoking cessation, diabetes control, weight loss, asthma self-management.[16] Tailored text-message based interventions may benefit EMS worker sleep habits and behaviors related to fatigue. Text-message interventions are a potentially high-impact, low-cost platform for encouraging positive sleep habits, tracking fatigue, and distributing information to EMS workers at risk of negative safety outcomes related to fatigue. In the first known study using text-messaging to study fatigue in EMS, we have 1) shown it is feasible to use this tool to monitor fatigue in real-time, and 2) produced early evidence that we can reduce perceived fatigue by intervening with tailored fatigue reduction strategies in real-time.

Research Protocol, Part Two – Objectives Hypotheses (3000 characters):

The overarching goal of this proposal is to address the MedEvac foundation priority of educational techniques and technologies to improve safety, and determine if an enhanced SleepTrackTXT intervention, including a sleep health component, reduces fatigue during shift work and leads to clinically meaningful improvements in sleep quality.

Aim 1: To determine the short-term impact of an enhanced SleepTrackTXT intervention on HEMS clinician fatigue reported in real-time during and at the end of shift work.

Rationale Aim 1: In our recent SleepTrackTXT pilot randomized trial, we have successfully shown that real-time assessment of fatigue involving EMS clinicians and text-messages is possible. We have also shown that sending text-messages in real-time to clinicians that report high levels of fatigue leads to reduced fatigue by the end of shift. An enhanced intervention that addresses additional sleep health information (e.g., sleep debt), may have a greater impact.

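### The stated Aim 1 mixed model has no arm term, and the plan does not say which between-arm contrast will be tested

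*Combined protocol and SAP*

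**What the plan says.** Research Protocol, Part Four (Outcome Measures & Data Analysis) says that linear mixed models will examine the effectiveness of the intervention on end-of-shift fatigue "and compare reported values to the control group". The next sentence states the model: the outcome is fatigue at the end of each shift, with "a fixed effect of time in study, and a random effect for participants to account for multiple shifts within each person". The plan then says it will look at how fatigue changes from shift to shift and across many shifts, and will describe within-person correlation. Neither of these sentences mentions arm, and arm is not in the list of independent measures.

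The hypotheses are worded in different ways:

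- **Part Two, Aim 1:** the "short-term impact of an enhanced SleepTrackTXT intervention on HEMS clinician fatigue". In the Abstract, Aim 2 is the one labelled long-term.
- **Part Two, Rationale for Aim 1:** sending messages in real time "leads to reduced fatigue by the end of shift".
- **Part Two, Hypothesis 1A:** the tool "will contribute to significant reductions in intra-shift fatigue", with no comparator or time point.
- **Part Four:** "over time and after repeated exposure to the intervention", the intervention group "will report lower levels of fatigue at the end of shift than participants in the control group".

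**The concern.** This is a two-arm randomized trial, and the comparison it promises for Aim 1 has no parameter in the model it states. Adding arm is the obvious repair, but it leaves at least three candidate tests: the arm difference averaged over the study, the difference in time trend (arm x time), and the arm difference late in the study. They estimate different things and can give different answers from the same data. If none is named beforehand, the choice can be made after the results are seen, and a reader of the report could not tell whether it was.

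**Working it through.** **Step 1. What the stated model can estimate.** As written, it is fatigue = b0 + b1 × time + participant effect + error. Arm does not appear, so exchanging the arm labels cannot change the fit. A simulated data set shows this (assumed: 100 participants, 30 shifts each, participant SD 0.8, residual SD 1, true arm x time effect −0.6):

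| Model | Estimates |
|---|---|
| As written | intercept 2.08, time −0.26; identical after swapping arms |
| Plus arm | arm −0.32 (p = 0.041) |
| Plus arm and arm x time | arm x time −0.39 (p = 0.0015); arm at time zero −0.12 (p = 0.47) |

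The stated model has nothing to test, and the added term determines the estimate and the p-value.

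**Step 2. Which contrast the wording supports.** The short-term aim and the within-shift rationale describe an effect that could be present from the first shifts; they suit an average difference. The Part Four hypothesis (lower levels after repeated exposure) and the sentence on change across shifts lean towards arm x time or a late-study difference. No sentence settles it.

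**Step 3. How much the choice could matter.** The plan gives no effect size, variance or power for Aim 1, so there is no figure to reproduce.

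*From the documents:* 50 per arm. On dropout, "We estimate a 15% attrition rate based on our prior randomized trial", which leaves 50 × 0.85 = 42.5 per arm if dropouts contribute nothing. The pilot recorded 2,621 shifts from 100 people in 90 days, about 26 each, or 26.2 × 120/90 = 35 over 4 months.

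*Assumed:* residual SD 1.0; intercept SD 0.8; slope SD 0.5 (between-person SD of change over 4 months); intercept–slope correlation zero; arm difference of 0.5 points at 4 months on the 0–5 scale; two-sided 5% test.

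With time running from 0 to 1, m = 26 evenly spread shifts and n = 50 per arm, SE = √(2V/n), where V is:

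- Arm x time: 0.5² + 12/26 = 0.7115; SE 0.169
- Average difference: 0.8² + 0.5²/4 + 1/26 = 0.7410; SE 0.172
- 4-month difference: 0.8² + 0.5² + 4/26 = 1.0438; SE 0.204

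Power is approximately Φ(effect/SE − 1.96). If the effect grows linearly from zero, the three effects are 0.5, 0.25 and 0.5. If it is constant, they are 0, 0.5 and 0.5.

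| Setting | Arm x time | Average | 4-month |
|---|---|---|---|
| Growing, 50 per arm | 84% | 31% | 69% |
| Constant, 50 per arm | 5% | 83% | 69% |
| Growing, 42.5 per arm | 78% | 27% | 62% |
| Constant, 42.5 per arm | 5% | 76% | 62% |

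Over 15–35 shifts and slope SD 0–0.8, with 50 per arm, the ranges are 55–99% / 27–33% / 52–82% (growing) and 5% / 77–86% / 52–82% (constant).

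Two further checks use 26 shifts, slope SD 0.5 and 50 per arm:

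- *Correlation.* An intercept–slope correlation of −0.5 or +0.5 changes V for the 4-month difference by 2 × 0.5 × 0.8 × 0.5 = 0.4 down or up. Power becomes about 88% or 55% instead of 69%.
- *Waning effect.* If the difference falls from 0.5 to 0.25, the average is 0.375 and power for the average difference is about 59%. The 4-month difference has about 23%. Arm x time then points against the intervention.

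**Step 4. Error if the choice stays open.** With no true effect, the chance that at least one of the three contrasts reaches two-sided p < 0.05 is 10.2–11.2% over 15–35 shifts and slope SD 0–0.8. Of this, 5.1–5.7 percentage points favour the intervention, against a nominal 2.5.

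**Step 5. Why a random slope belongs in the model.** The plan states a random effect for participants without saying whether it includes a slope. In simulated unbalanced trials (10–35 shifts per person, 2,000 trials per setting), the type I error of arm x time was:

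| Slope SD | 0 | 0.3 | 0.5 | 0.8 |
|---|---|---|---|---|
| Random intercept only | 5.0% | 6.7% | 10.4% | 18.8% |
| With random slope | 4.6% | 4.8% | 5.2% | 5.5% |

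**The case against.** The best defence is that this is a drafting omission in a section limited to 3000 characters. The sentence before the model says the arms will be compared, and a competent analyst would add arm. That stands. A reader might infer that the plan contains no between-arm analysis of Aim 1, but the documents do not support that: the comparison is declared, and what is missing is its parameter.

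A second defence is that the sentence on change from shift to shift shows which estimate matters and points to arm x time. It does lean that way, so the three candidates are not equally supported. But it does not mention arm, and it sits beside a hypothesis about level and an aim called short-term. It does not settle the contrast.

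Third, the figures rest on assumptions. That is also right. The zero intercept–slope correlation and the shape of the effect matter as much as the variances, the base case uses the 90-day shift count, and the plan's separate 15% non-compliance estimate is not included. The figures show that the choice can be decisive; they do not predict this trial's power.

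A reader might also infer that the 4-month difference is the right test because its power is the same in the growing and constant cases. That follows only from fixing the 4-month difference at 0.5 in both; the waning case removes the advantage. An end-of-study test also fits poorly with an aim called short-term. The documents do not point to one correct contrast, so the choice belongs to the sponsor.

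**Conclusion.** The point holds and should be fixed. Two parts need no assumption: the model as stated cannot estimate or test the intervention effect, and no section names the contrast. In the illustration, arm x time and the average difference change places (84% against 31%, then 5% against 83%) according to whether the effect builds up or is constant, but these sizes depend on the assumed variances, effect shape and zero intercept–slope correlation.

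A reader might infer that the trial's false-positive rate for Aim 1 is 10–11%. The documents do not support that. The figure applies only if any of the three contrasts could be claimed as the result, and nothing in the plan says that it will be. The random-slope point is likewise conditional: it matters only if time enters the contrast and participants' trends differ, and the plan does not rule out a random slope. The trial is not invalidated, since the data to be collected support any of these tests.

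**What to change.** Replace the model sentence in Part Four with wording such as:

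> End-of-shift fatigue will be modelled with fixed effects of arm, time in study and arm x time, and with a participant random intercept and random slope for time. The Aim 1 test is [one of: the average arm difference over the study; the arm x time coefficient; the arm difference at a stated time point]. The other contrasts will be reported with 95% confidence intervals as supporting results.

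The sponsor should fill the bracket before any outcome data are seen by arm, and align the wording of Aim 1 and the Part Four hypothesis with the choice.

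The cost is analysis wording. No new data are needed, and the sample size is unaffected because it was derived from the PSQI. The downside is some precision for contrasts involving time. In the unbalanced simulations, adding the random slope raised the standard error of arm x time by about 3% when slopes were in fact equal (0.149 to 0.154). It left that of the 4-month difference unchanged at 0.182. At slope SD 0.5 the latter rose by 11% (0.188 to 0.208); there the smaller value was too optimistic, with 7.0% type I error against 4.8% with the slope included.
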